2 OBJECTIVES

2.1 Objectives

2.1.1 **Primary Objective**

To evaluate the PK profile of a single SC dose of 300 mg tralokinumab when delivered as a 2 mL injection at different flow rates to healthy adult volunteers

2.1.2 Secondary Objectives

- 1. To determine the local tolerability and overall safety profile of a single SC dose of 300 mg tralokinumab when delivered as a 2 mL injection at different flow rates
- 2. To determine the immunogenicity profile of a single SC dose of 300 mg tralokinumab when delivered as a 2 mL injection at different flow rates

2.1.3 Exploratory Objectives

To determine the effect of a single SC dose of 300 mg tralokinumab when delivered as a single 2 mL injection at different flow rates in healthy volunteers on biomarkers relevant to the mechanism of action of tralokinumab

2.2 Study Endpoints

2.2.1 Primary Endpoint

The primary endpoint is the PK profile of tralokinumab.

2.2.2 Secondary Endpoint(s)

- 1. Local injection site pain intensity and injection site pruritus post-injection
- 2. Local injection site reactions (eg, erythema, bleeding, rash, etc) post-injection
- 3. Presence of fluid leakage immediately post-injection
- 4. Incidence of TEAEs including clinically significant changes in vital signs, physical examinations, and laboratory parameters

5. Presence of ADA to tralokinumab

2.2.3 Exploratory Endpoint(s)

Assessment of biomarkers (including periostin and dipeptidyl peptidase-4 [DPP-4]) relevant to the mechanism of action of tralokinumab

3 STUDY DESIGN

3.1 Description of the Study

3.1.1 Overview

This is a Phase 1, open-label, assessor-blind, parallel-group study to evaluate the PK and tolerability of a single SC dose of 300 mg tralokinumab when delivered as a 2 mL injection at different flow rates to healthy adult volunteers. A total of 60 subjects at one site in the

will be randomized in a 1:1:1:1 ratio to 1 of 4 cohorts to receive a single SC dose of 300 mg tralokinumab. Due to the potential for gender differences in pain perception and sensitivity (Wisenfeld-Hallin, 2005; Paller et al, 2009), randomization, will be stratified by gender. A minimum of 5 males and 5 females will be randomized to each cohort; the additional subjects may be of either sex. All injections will be administered SC in

the abdomen using a syringe pump and SC insertion set at the following flow rates:

- Cohort 1: 2 × 1 mL SC injections, with each injection administered at a rate of 6 mL/minute (min)
- Cohort 2: 1 × 2 mL SC injection administered at a rate of 12 mL/min
- Cohort 3: 1×2 mL SC injection administered at a rate of 2 mL/min
- Cohort 4: 1×2 mL SC injection administered at a rate of 0.167 mL/min

A screening visit will be performed within 21 days prior to dosing. Subjects will be admitted to the study unit on Day -1. Following administration of 300 mg tralokinumab on Day 1, subjects will be followed up for 57 days for safety, tolerability, immunogenicity, and PK sampling. A study flow diagram is presented in Figure 3.1.1-1.

Subjects will be in this study for up to 79 days, which includes a screening/consent period of up to 21 days, a 1-day treatment period, and a 57-day post-treatment follow-up period.

The endpoints to be measured in this study are described in Section 2.2.

Figure 3.1.1-1 Study Flow Diagram

IP = investigational product; min = minute; N = number of subjects.

3.1.2 Treatment Regimen

A total of 60 subjects will be randomized in a 1:1:1:1 ratio to 1 of 4 cohorts to receive a single SC dose of tralokinumab as described in Table 3.1.2-1. Randomization will be stratified by gender. At a minimum, 5 males and 5 females will be randomized to each cohort; the additional subjects may be of either sex.

Table 3.1.2-1 Investigational Product Dose and Treatment Regimen

Cohort	Ν	Day 1	
1	15	300 mg tralokinumab as 2×1 mL SC injections, with each injection administered at a flow rate of 6 mL/min	
2	15	300 mg tralokinumab as a 1×2 mL SC injection administered at a flow rate of 12 mL/min	
3	15	300 mg tralokinumab as a 1×2 mL SC injection administered at a flow rate of 2 mL/min	
4	15	300 mg tralokinumab as a 1×2 mL SC injection administered at a flow rate of 0.167 mL/min	

N = number of subjects; SC = subcutaneous.

All injections will be administered into the abdomen via the SC route at the flow rates specified above using a syringe pump and SC insertion set.

3.2 Study Design and Dose Rationale

3.2.1 Dose Rationale

In a previous study in subjects with asthma (Study MI-CP199), treatment with 300 mg tralokinumab Q2W was well-tolerated and showed an effect on FEV₁. Doses lower than 300 mg were found to result in suboptimal increase in FEV₁; therefore, this dose is considered the most appropriate to determine the effect of modulating the dosing administration regimen for the current study. However, tralokinumab is formulated at a concentration of 150 mg/mL and currently requires 2×1 mL SC injections to deliver the target dose. Development of an alternative method to support delivery of larger volumes of tralokinumab (via large volume bolus injector or large volume autoinjector) is planned to enable the target dose to be delivered via a single injection rather than 2 separate injections.

3.2.2 Rationale for Study Population

The aim of this study is to evaluate the PK and tolerability of a single SC dose of 300 mg tralokinumab. No efficacy outcomes are planned and the likelihood of clinical benefit for an asthma subject following a single dose of tralokinumab is low based on previous data and modeling predictions. Therefore, healthy adult volunteers have been chosen to aid retention and ensure that the primary study objectives are met. The use of this population is further

supported by data from PK modeling, which has demonstrated that there is no effect of the presence or absence of asthma on the PK profile of tralokinumab, and provides confidence in the applicability of the results.

3.2.3 Rationale for Endpoints

Primary Endpoint

The primary endpoint of the study is the PK of tralokinumab. Each subject will receive a single dose of 300 mg tralokinumab by one of 4 administration regimens and 57 days of follow up. Based on prior data, the maximum concentration $_{(Cmax)}$ of tralokinumab usually occurs between 2-9 days with a half-life of approximately 21 days following SC administration. Therefore, the sampling scheme will provide adequate samples for the characterization of $_{Cmax}$ and area under the serum concentration-time curve (AUC) parameters through noncompartmental analysis. The PK parameters associated with a single 2 mL injection of tralokinumab at different flow rates will be compared to those associated with 2×1 mL injections of tralokinumab to determine the feasibility of larger volume delivery and to provide information to aid in the design of the final device.

Secondary Endpoints

Injection site pain will be measured using a 100 mm visual analogue scale (VAS; see Appendix 4). Local injection-site tolerability parameters will also be measured, including injection-site itch and visual assessment of the injection site for reactions such as erythema, rash, etc. As local injection-site reactions are of specific interest, they will be recorded in detail on a dedicated and standardized injection-site questionnaire (Appendix 2) at each time point post-injection. These targeted assessment events will not require reporting as adverse events (AEs) on the AE electronic case report form (eCRF), unless they meet one or more of the following criteria:

- Fulfils the criteria for a serious adverse event (SAE)
- Leads to premature termination of the injection during investigational product administration
- Requires concomitant medication or other medically important intervention
- Has an impact on the general condition of the subject as judged by the investigator

These data will be used to determine the overall tolerability of a single 2 mL injection of tralokinumab at different flow rates to determine the feasibility of this approach compared to 2×1 mL injections and to provide information to aid in the design of the final delivery device.

The degree of fluid leakage from the injection site will be assessed immediately following all injections to determine if the flow rates affect delivery of the 2 mL injection volume.

Adverse events and immunogenicity of tralokinumab will also be reported to ensure ongoing monitoring of the safety profile for this investigational product.

Exploratory Endpoints

Serum for assessment of biomarkers relevant to the mechanism of action of tralokinumab, including periostin and DPP-4 levels, will be collected to establish reference values in healthy individuals to compare with prior data collected from subjects with asthma in previous studies and to determine if these levels change following treatment with tralokinumab in this subject group. These data will be analyzed separately by the sponsor.

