- ^f Local injection-site reactions are of specific interest and will be recorded in detail on dedicated and standardized injection site assessment questionnaire (see Appendix 2) at each time point post-injection. These targeted assessment events will not require reporting as AEs on the AE eCRF, unless they meet 1 or more of the following criteria:
 - Fulfils the criteria for an SAE
 - Leads to premature termination of the injection during investigational product administration
 - Requires concomitant medication or other medically important intervention
 - Has an impact on the general condition of the subject as judged by the investigator
- ^g Local injection site reactions (eg, erythema, bleeding, rash, etc) will be assessed by a blinded assessor immediately post-injection (after the second injection in Cohort 1) and at 10, 20, 30, and 60 minutes and then at 2, 4, and 8 hours post-injection for all 4 cohorts

	Prior to IP Admin	During IP Administration		Post IP Administration								
Assessment		1 Min (Cohort 4 only)	6 Min (Cohort 4 only)	Immediately	10 Min (~ 3 min)	20 Min (~ 3 min)	30 Min (~ 3 min)	60 Min (~ 3 min)	2 Hours (~ 10 min)	4 Hours (~ 10 min)	8 Hours (~ 10 min)	
Randomization	X											
Physical examination	X											
Weight	Х											
AEs/SAEs	X	Х	X	X	Х	X	Х	Х	Х	Х	Х	
Concomitant medications	X	Х	X	Х	Х	X	Х	Х	X	X	X	
Vital signs	X			X	Х		Х	Х		Х	X	
Collect blood for:												
РК	X											
IM	X											
Biomarkers	X											
Assess injection site	for:											
Fluid leakage/ gravimetric analysis				Х								
Pain intensity via VAS		Х	X	Х	Х	X	Х	Х	X	X	X	
Pruritus via VAS				X	Х	X	X	X	X	X	X	
Local injection- site reactions ^b				X	X	X	X	X	X	X	X	

Admin = administration; AE = adverse event; IM = immunogenicity; IP = investigational product; Min/min = minute(s); PK = pharmacokinetic; SAE = serious adverse event; VAS = visual analog scale.

^a Injection sites must be assessed in the following order at *all time points* post administration of IP: visual inspection for fluid leakage (immediately post-injection only); VAS scale for pain intensity; VAS scale for pruritus; assessment for local injection-site reactions as outlined in Table 4.2.2-2.

^b Local injection-site reactions to be evaluated by blinded assessor.

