4.3.3 Injection Site Assessments

The injection site(s) will be assessed for pain intensity, pruritus, local injection-site reactions, and fluid leakage. For Cohort 1, assessments will begin after the second 1 mL injection has been administered. The subject will assess injection-site pain intensity and pruritus using a VAS as described in Section 4.3.3.2 and Section 4.3.3.3 and a blinded assessor will assess local injection site reactions as described in Section 4.3.3.4. The investigator or qualified designee will assess investigational product leakage as described in Section 4.3.3.1.

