4.3.3.1 Investigational Product Leakage

The investigator or qualified designee will visually examine the injection site for investigational product leakage immediately following the injection, once the needle insertion set has been withdrawn, on Day 1 as outlined in Table 4.2.2-1 and Table 4.2.2-2.

If leakage is present, the injection site will be blotted with pre-weighed absorbent material and the amount of leakage will be quantified and recorded. For subjects in Cohort 1 who will receive 2×1 mL injections of tralokinumab, the overall assessment of fluid leakage from both injection sites combined should be recorded immediately post-injection.

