4.6.2 Methods for Ensuring Blinding

Both site and sponsor personnel will be unblinded, with the exception of a blinded injection-site assessor who will evaluate local reactions to investigational product administration. The blinded injection-site assessor will be unaware of the treatment allocation

of all subjects where practicably possible (eg, for subjects randomized to Cohort 1, the requirement for 2 separate injections makes blinding to treatment allocation impossible) and will not observe the preparation or administration of investigational product or participate in the conduct of the study outside of the injection-site assessments (see Section 4.3.3.4).

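### Leakage is weighed only after staff who know the flow rate judge by eye that it is present, so recorded leakage can differ between cohorts through detection alone

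*Protocol*

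**What the plan says.** Section 2.2.2 lists as secondary endpoint 3 "Presence of fluid leakage immediately post-injection". Section 3.2.3 states why it is collected: "The degree of fluid leakage from the injection site will be assessed immediately following all injections to determine if the flow rates affect delivery". The delivery meant there is that of the single larger-volume injection.

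Section 4.3.3.1 sets out the procedure in two steps. First, detection by eye: "The investigator or qualified designee will visually examine the injection site for" leakage, once the insertion set is out. Second, measurement, on a condition: "If leakage is present, the injection site will be blotted with pre-weighed absorbent material and the amount of leakage will be quantified and recorded". For Cohort 1 the two sites are recorded as one combined assessment.

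On who does this, Section 4.3.3 gives local reactions to the blinded assessor but says of leakage: "The investigator or qualified designee will assess investigational product leakage as described in Section 4.3.3.1". Section 4.6.2 states: "Both site and sponsor personnel will be unblinded, with the exception of a blinded injection-site assessor who will evaluate local reactions". Section 4.6.1 makes allocation open label.

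On order, footnote a to the Day 1 timing table (Table 4.2.2-2) starts with "visual inspection for fluid leakage (immediately post-injection only); VAS scale for pain intensity; VAS scale for pruritus", followed by the reaction assessment. Section 4.8.4.1 summarizes leakage by cohort without a statistical test.

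**The concern.** The objective part of the measurement, the weight gain of a pre-weighed pad, exists only for sites that have already passed a subjective gate. The person at the gate knows the flow rate, and flow rate is the factor being compared. If that knowledge changes how hard someone looks, or how readily a faint trace is called, the cohorts will differ in recorded leakage even when true leakage is the same. A leak that is not called has no weight, so the amount depends on the same gate.

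The protocol protects the visual scoring of local reactions with a blinded assessor where that is practicable, but gives the visual call on leakage no such protection. What is at stake is the cohort comparison on this endpoint. To a lesser degree it is also the use of leaked volume to interpret any pharmacokinetic difference between cohorts, since leaked drug is drug not delivered.

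This is not detail that a statistical analysis plan would normally supply. It is the measurement procedure, and Section 4.3.3.1 fixes it.

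**Working it through.** **Figures in the protocol.** The protocol gives no leakage rate, detection rate or expected leaked volume. Its only power figure (Section 4.8.2) concerns AUC: 84% for a 1.5-fold difference, 15 per cohort, CV 37%, two-sided t-test at 0.05. On the log scale the difference is ln(1.5). With SD = sqrt(ln(1 + 0.37²)) = 0.358 the power is 84.9%; with SD = 0.37 it is 82.6%. The figure reproduces, but it says nothing about leakage.

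**The chain of text.**
1. Presence of leakage is a visual call by the investigator or designee (4.3.3, 4.3.3.1).
2. That person is not the blinded assessor, whose role is confined to local reactions (4.3.3.4, 4.6.2), and so is unblinded.
3. Weighing follows only a positive call (4.3.3.1).
4. Hence presence is an unblinded judgement. The weight is objective once taken, but whether it is taken depends on that judgement.

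**What one subject is worth.** 1/15 = 6.7 percentage points of incidence in a cohort.

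**Illustration on assumed values.** If the true share of leaking subjects, p, is the same in two cohorts and detection is d1 and d2, the false difference is p × (d1 − d2). Neither p nor d comes from the document.

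| True share p | Equal detection | 90% vs 60% | 90% vs 30% |
|---|---|---|---|
| 20% | 0 points | 6 points (2.7 vs 1.8 of 15) | 12 points (2.7 vs 0.9) |
| 40% | 0 points | 12 points (5.4 vs 3.6) | 24 points (5.4 vs 1.8) |
| 60% | 0 points | 18 points (8.1 vs 5.4) | 36 points (8.1 vs 2.7) |

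The result is driven wholly by the assumed gap in detection.

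**Order relative to the first VAS.** Footnote a names only visual inspection ahead of the pain score. The table row, however, pairs fluid leakage with gravimetric analysis, marks it only at the immediate time point, sits above the pain row and has no later slot. Blotting before the first VAS is the natural reading but is not stated.

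**A check on the remedy.** If every site is blotted and presence means any pad above a per-pad limit, Cohort 1 has two chances of a false positive. At an assumed false-positive rate of 10% per pad, Cohort 1 would show 1 − 0.90² = 19% against 10% in the other cohorts. The threshold therefore has to be set for the two-site total in Cohort 1.

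**The case against.** Sections 3.2.3 and 4.3.3.1 do not contradict each other. Every site is inspected after every injection, leaks are quantified, and a dry site has degree zero. Visible fluid is a fairly concrete sign, and missing a large share of leaks is hard to square with an inspection made for that purpose. A weight once taken is objective, and an overlooked trace matters little to delivery of 2 mL. Leakage is only summarized descriptively in a study that Section 1.5 calls exploratory, and limiting blinding to local reactions is a declared choice. All of this stands, and it confines the point to small or trace leaks. It does not remove the gate: a descriptive comparison of cohorts is still a comparison.

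Three stronger readings are tempting and are not supported.
- A reader might infer that leakage will be over-called at the fast rates. No section predicts leakage by flow rate; Section 3.2.3 asks whether there is an effect, and the secondary hypotheses in Section 1.6.2 cover pain, pruritus and local reactions only.
- A reader might take gaps like those in the table as the expected bias. They rest on assumed detection rates.
- A reader might conclude that only leaking sites are handled before the first pain score. The order of blotting is inferred. Moreover, every subject has just had an insertion set withdrawn, and nothing in the document shows that a brief blot changes a VAS score.

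**Conclusion.** The point holds in a limited form. Under Section 4.3.3.1 an unblinded visual judgement decides both recorded presence and whether an amount is measured, although comparing flow rates is the stated purpose of the endpoint. Recorded leakage can therefore differ by cohort through detection, mainly for small or trace leaks.

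Direction and size cannot be derived from the protocol. The only figure that rests on its own numbers is 6.7 points of incidence per misjudged subject; with equal detection across cohorts the false difference is zero. Whether blotting comes before the first VAS is suggested by Table 4.2.2-2 but left unstated. This is a cheap improvement to the measurement plan, not an error that invalidates the endpoint.

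**What to change.** In Section 4.3.3.1 and Tables 4.2.2-1 and 4.2.2-2:
- Blot every injection site in every cohort once, in the same way, with pre-weighed material right after set withdrawal, whether or not fluid is visible. State that this comes before the first VAS.
- Report the weight gain as a continuous amount for all subjects.
- Define presence by a threshold fixed in advance from blank pads applied to comparable dry, prepared skin. Balance resolution will not serve: it describes the instrument and would count sweat, residual alcohol or blood as leakage.
- Set the threshold for the combined two-site total in Cohort 1, so that two pads do not raise its false-positive rate.
- Keep the visual call as a descriptive item.
- Record any visible blood on the pad, so that the leakage weight and the later bleeding score can both be interpreted.

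The cost is small. There are 15 × 2 + 45 × 1 = 75 sites, so at most 75 pads and weighings, fewer those the present rule already requires, plus the blank pads and a few lines of text. The gravimetric step is already in the protocol. The remaining downside is slight noise from moisture.

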4 MATERIALS AND METHODS

4.1 Subjects

4.1.1 Number of Subjects

A total of 60 subjects will be randomized in a 1:1:1:1 ratio to 1 of 4 cohorts to receive a single SC dose of 300 mg tralokinumab administered as either 2×1 mL SC injections at a flow rate of 6 mL/min for each injection (Cohort 1) or a 1×2 mL SC injection at flow rates of 12, 2, or 0.167 mL/min (Cohorts 2, 3, or 4, respectively). At minimum, 5 males and 5 females will be randomized to each cohort; the additional subjects may be of either sex.

4.1.2 Inclusion Criteria

Subjects must meet all of the following criteria:

- 1. Healthy males and females ages 19-65 years inclusive at the time of screening
- 2. Written informed consent and any locally required authorization obtained from the subject prior to performing any protocol-related procedures, including screening evaluations
- 3. Body mass index of 19.0-30.0 kg/m
- 4. Intact normal skin without potentially obscuring tattoos, scars, pigmentation, or lesions on the abdominal area intended for injection
- 5. No clinically significant abnormality on the basis of medical/medication history or physical examination
- 6. Vital signs, electrocardiogram (ECG), and laboratory parameters within normal range, or if outside normal range deemed not clinically significant by the Principal Investigator or medical monitor

- 7. Negative alcohol and drug screens
- 8. Able and willing to comply with the requirements of the protocol
- 9. Females of childbearing potential who are sexually active (ie, do not practice complete abstinence) with a nonsterilized male partner must use highly effective contraception (confirmed by the investigator) from screening, and must agree to continue using such precautions until 3 months after the day of dosing; cessation of contraception after this point should be discussed with a responsible physician. Periodic abstinence, the rhythm method, and the withdrawal method are not acceptable methods of contraception. Females must have a negative pregnancy test at the time of screening and prior to randomization for inclusion in the study.
 - Females of childbearing potential are defined as those who are not surgically sterile (ie, have not undergone bilateral tubal ligation, bilateral oophorectomy, or complete hysterectomy) or postmenopausal (defined as 12 months with no menses without an alternative medical cause and follicle-stimulating hormone [FSH] levels consistent with menopausal status).
 - A highly effective method of contraception is defined as one that results in a low failure rate (ie, less than 1% per year) when used consistently and correctly. The acceptable methods of contraception are described in Table 4.1.2-1.
- 10. Nonsterilized males who are sexually active with a female partner of childbearing potential must use highly effective contraception (see Table 4.1.2-1) from screening until 3 months after the day of dosing; cessation of contraception after this point should be discussed with a responsible physician.

 Table 4.1.2-1
 Highly Effective Methods of Contraception

	Barrier Methods		Hormonal Methods
•	Male condom plus spermicide	•	Implants
•	Copper T intrauterine device	•	Hormone shot or injection
•	Levonorgestrel-releasing intrauterine system (eg,	•	Combined pill
	Mirena®) ^a	•	Minipill
		•	Patch

This is also considered a hormonal method.

